11. CHANGES TO PROTOCOL-SPECIFIED ANALYSES AND ENDPOINTS

Gut microbiome and genetic samples will potentially be analyzed. Details of this analysis will be included in a separate SAP.

13. APPENDICES

APPENDIX A. LIST OF TABLES, FIGURES, AND LISTINGS

List of Tables

| Table Number | Population | Table Title |
|--------------|-------------------------|--|
| 14.1 | | Demographic Data |
| 14.1.1 | All Randomized Subjects | Summary of Analysis Populations During |
| 14.1.2 | ITT | Summary of Subject Disposition |
| 14.1.3 | ITT | Summary of Protocol Deviations |
| 14.1.4.1 | ITT | Summary of Demographics and Baseline Characteristics |
| 14.1.4.2 | PK | Summary of Demographics and Baseline Characteristics |
| 14.1.4.3 | Safety | Summary of Demographics and Baseline Characteristics |
| 14.1.4.4 | W12C | Summary of Demographics and Baseline Characteristics |
| 14.1.4.5 | W24C | Summary of Demographics and Baseline Characteristics |
| 14.1.4.6 | ITT | Summary of Demographics and Baseline Characteristics by IBD Status |
| 14.1.4.7 | ITT | Summary of Demographics and Baseline Characteristics by UC Status |
| 14.1.4.8 | ITT | Summary of Demographics and Baseline Characteristics by CD Status |
| 14.1.4.9 | ITT | Summary of Demographics and Baseline Characteristics by Baseline BMI |
| 14.1.4.10 | ITT | Summary of Demographics and Baseline Characteristics by Baseline UDCA Use |
| 14.1.4.11 | ITT | Summary of Demographics and Baseline Characteristics by Baseline Total Bilirubin |
| 14.1.4.12 | ITT | Summary of Demographics and Baseline Characteristics by Gender |
| 14.1.4.13 | ITT | Summary of Demographics and Baseline Characteristics by Baseline TE Score |
| 14.1.5.1 | ITT | Summary of PSC Disease History |
| 14.1.5.2 | W12C | Summary of PSC Disease History |
| 14.1.5.3 | W24C | Summary of PSC Disease History |
| 14.1.5.4 | ITT | Summary of PSC Disease History by IBD Status |
| 14.1.5.5 | ITT | Summary of PSC Disease History by UC Status |

| | | |
|-------------|------|--|
| 14.1.5.6 | ITT | Summary of PSC Disease History by CD Status |
| 14.1.5.7 | ITT | Summary of PSC Disease History by Baseline BMI |
| 14.1.5.8 | ITT | Summary of PSC Disease History by Baseline UDCA Use |
| 14.1.5.9 | ITT | Summary of PSC Disease History by Baseline Total Bilirubin |
| 14.1.5.10 | ITT | Summary of PSC Disease History by Gender |
| 14.1.5.11 | ITT | Summary of PSC Disease History by Baseline TE Score |
| 14.1.6 | ITT | Summary of Abnormal Medical History at Baseline |
| 14.2 | | Efficacy Data |
| 14.2.1.1 | W24C | Summary of Alkaline Phosphatase by Treatment and Visit |
| 14.2.1.2 | W12C | Summary of Alkaline Phosphatase by Treatment and Visit |
| 14.2.1.3 | ITT | Summary of Alkaline Phosphatase by Treatment and Visit |
| 14.2.1.4 | ITT | Summary of Alkaline Phosphatase by Baseline Antibiotic Use, Treatment, and Visit |
| 14.2.1.5 | ITT | Summary of Alkaline Phosphatase by IBD Status, Treatment, and Visit |
| 14.2.1.6 | ITT | Summary of Alkaline Phosphatase by UC Status, Treatment, and Visit |
| 14.2.1.7 | ITT | Summary of Alkaline Phosphatase by CD Status, Treatment, and Visit |
| 14.2.1.8 | ITT | Summary of Alkaline Phosphatase by Baseline BMI, Treatment and Visit |
| 14.2.1.9 | ITT | Summary of Alkaline Phosphatase by Baseline UDCA Use, Treatment and Visit |
| 14.2.1.10 | ITT | Summary of Alkaline Phosphatase by Baseline Total Bilirubin, Treatment and Visit |
| 14.2.1.11 | ITT | Summary of Alkaline Phosphatase by Gender, Treatment and Visit |
| 14.2.1.12 | ITT | Summary of Alkaline Phosphatase by Baseline Median TE Score, Treatment and Visit |
| 14.2.2.1 | ITT | Summary of Alkaline Phosphatase by Treatment and Visit (MMRM) |
| 14.2.3.1.1 | W24C | Summary of Subjects with Alkaline Phosphatase < 1.5 x Upper Limit of Normal by Treatment and Visit |
| 14.2.3.1.2 | W12C | Summary of Subjects with Alkaline Phosphatase < 1.5 x Upper Limit of Normal by Treatment and Visit |
| 14.2.3.1.3 | ITT | Summary of Subjects with Alkaline Phosphatase < 1.5 x Upper Limit of Normal by Treatment and Visit |

| | | |
|------------|------|---|
| 14.2.3.2.1 | W24C | Summary of Subjects with $\geq 10\%$ Reduction from Baseline in Alkaline Phosphatase by Treatment and Visit |
| 14.2.3.2.2 | W12C | Summary of Subjects with $\geq 10\%$ Reduction from Baseline in Alkaline Phosphatase by Treatment and Visit |
| 14.2.3.2.3 | ITT | Summary of Subjects with $\geq 10\%$ Reduction from Baseline in Alkaline Phosphatase by Treatment and Visit |
| 14.2.3.3.1 | W24C | Summary of Subjects with $\geq 15\%$ Reduction from Baseline in Alkaline Phosphatase by Treatment and Visit |
| 14.2.3.3.2 | W12C | Summary of Subjects with $\geq 15\%$ Reduction from Baseline in Alkaline Phosphatase by Treatment and Visit |
| 14.2.3.3.3 | ITT | Summary of Subjects with $\geq 15\%$ Reduction from Baseline in Alkaline Phosphatase by Treatment and Visit |
| 14.2.3.4.1 | W24C | Summary of Subjects with $\geq 20\%$ Reduction from Baseline in Alkaline Phosphatase by Treatment and Visit |
| 14.2.3.4.2 | W12C | Summary of Subjects with $\geq 20\%$ Reduction from Baseline in Alkaline Phosphatase by Treatment and Visit |
| 14.2.3.4.3 | ITT | Summary of Subjects with $\geq 20\%$ Reduction from Baseline in Alkaline Phosphatase by Treatment and Visit |
| 14.2.3.5.1 | W24C | Summary of Subjects with $\geq 25\%$ Reduction from Baseline in Alkaline Phosphatase by Treatment and Visit |
| 14.2.3.5.2 | W12C | Summary of Subjects with $\geq 25\%$ Reduction from Baseline in Alkaline Phosphatase by Treatment and Visit |
| 14.2.3.5.3 | ITT | Summary of Subjects with $\geq 25\%$ Reduction from Baseline in Alkaline Phosphatase by Treatment and Visit |
| 14.2.3.6.1 | W24C | Summary of Subjects with $\geq 30\%$ Reduction from Baseline in Alkaline Phosphatase by Treatment and Visit |
| 14.2.3.6.2 | W12C | Summary of Subjects with $\geq 30\%$ Reduction from Baseline in Alkaline Phosphatase by Treatment and Visit |
| 14.2.3.6.3 | ITT | Summary of Subjects with $\geq 30\%$ Reduction from Baseline in Alkaline Phosphatase by Treatment and Visit |
| 14.2.3.7.1 | W24 | Summary of Subjects with $\geq 35\%$ Reduction from Baseline in Alkaline Phosphatase by Treatment and Visit |
| 14.2.3.7.2 | W12C | Summary of Subjects with $\geq 35\%$ Reduction from Baseline in Alkaline Phosphatase by Treatment and Visit |
| 14.2.3.7.3 | ITT | Summary of Subjects with $\geq 35\%$ Reduction from Baseline in Alkaline Phosphatase by Treatment and Visit |
| 14.2.3.8.1 | W24C | Summary of Subjects with $\geq 40\%$ Reduction from Baseline in Alkaline Phosphatase by Treatment and Visit |
| 14.2.3.8.2 | W12C | Summary of Subjects with $\geq 40\%$ Reduction from Baseline in Alkaline Phosphatase by Treatment and Visit |

| | | |
|-------------|-----|--|
| 14.2.3.8.3 | ITT | Summary of Subjects with $\geq 40\%$ Reduction from Baseline in Alkaline Phosphatase by Treatment and Visit |
| 14.2.4.1 | ITT | Summary of Hepatic Biochemistry and Indices of Function by Treatment and Visit – ANCOVA |
| 14.2.4.2 | ITT | Summary of Hepatic Biochemistry and Indices of Function by Treatment and Visit – MMRM |
| 14.2.5.1 | ITT | Summary of Markers of Hepatic and GI Inflammation and Disease by Treatment and Visit – ANCOVA |
| 14.2.5.2 | ITT | Summary of Markers of Hepatic and GI Inflammation and Disease by Treatment and Visit – MMRM |
| 14.2.6.1 | ITT | Summary of Transient Elastography by Treatment and Visit |
| 14.2.6.2 | ITT | Summary of Liver Fibrosis Improvement via Transient Elastography by Treatment |
| 14.2.6.3 | ITT | Summary of Enhanced Liver Fibrosis Score and Components by Treatment and Visit |
| 14.2.7 | ITT | Summary of Farnesoid X Receptor Activity by Treatment and Visit |
| 14.2.8.1 | ITT | Summary of Pruritus Visual Analogue Scale Scores by Treatment and Visit |
| 14.2.8.2 | ITT | Summary of Pruritus 5-D Itch Scores by Treatment and Visit |
| 14.2.8.3 | ITT | Summary of Partial Mayo Score by Treatment and Visit |
| 14.2.8.4 | ITT | Summary of Chron's Disease Activity Index Score by Treatment and Visit |
| 14.2.9.1 | ITT | Summary of Ulcerative Colitis Remission by Treatment and Visit |
| 14.2.9.2 | ITT | Summary of Mild Ulcerative Colitis by Treatment and Visit |
| 14.2.9.3 | ITT | Summary of Crohn's Disease Remission by Treatment and Visit |
| 14.2.10 | PK | Summary of Week 12 and 24 Plasma Concentrations for Unconjugated OCA, OCA, Glyco-OCA, Tauro-OCA, and Total OCA |
| 14.2.8 | PK | Summary of Week 12 and 24 Plasma PK Parameters for Unconjugated OCA, OCA, Glyco-OCA, Tauro-OCA, and Total OCA |
| 14.2.9.1 | PK | Summary of Total Bile Acids and Total Endogenous Bile Acids |
| 14.2.9.2 | PK | Summary of Bile Acids and Bile Acid Sub-components |
| 14.2.9.3 | PK | Summary of Bile Acid Proportions |
| 14.3 | | Safety Data |
| 14.3.1 | ITT | Summary of Investigational Product Exposure |
| 14.3.2.1 | ITT | Summary of Prior Concomitant Medications |

| | | |
|---------------|--------|--|
| 14.3.2.2 | ITT | Summary of New Concomitant Medications |
| 14.3.1 | | Displays of Adverse Events |
| 14.3.1.1 | Safety | Overall Summary of Treatment Emergent Adverse Events |
| 14.3.1.2.1 | Safety | Summary of Treatment Emergent Adverse Events by System Organ Class and Preferred Term |
| 14.3.1.2.2 | Safety | Summary of Treatment Emergent Adverse Events by Preferred Term |
| 14.3.1.3.1 | Safety | Summary of Investigational product-related Treatment Emergent Adverse Events by System Organ Class and Preferred Term |
| 14.3.1.3.2 | Safety | Summary of Investigational product-related Treatment Emergent Adverse Events by Preferred Term |
| 14.3.1.4.1 | Safety | Summary of Serious Adverse Events by System Organ Class and Preferred Term |
| 14.3.1.4.2 | Safety | Summary of Serious Adverse Events by Preferred Term |
| 14.3.1.5.1 | Safety | Summary of Treatment-Emergent Adverse Events Leading to Investigational Product Withdrawal or Study Discontinuation by System Organ Class and Preferred Term |
| 14.3.1.5.2 | Safety | Summary of Treatment-Emergent Adverse Events Leading to Investigational Product Withdrawal or Study Discontinuation by Preferred Term |
| 14.3.1.6.1 | Safety | Summary of Treatment-Emergent Adverse Events Leading to Investigational Product Withdrawal by System Organ Class and Preferred Term |
| 14.3.1.6.2 | Safety | Summary of Treatment-Emergent Adverse Events Leading to Investigational Product Withdrawal by Preferred Term |
| 14.3.1.7.1 | Safety | Summary of Treatment-Emergent Adverse Events Leading to Study Discontinuation by System Organ Class and Preferred Term |
| 14.3.1.7.2 | Safety | Summary of Treatment-Emergent Adverse Events Leading to Study Discontinuation by Preferred Term |
| 14.3.1.8.1 | Safety | Summary of Treatment Emergent Adverse Events by Maximum Severity, System Organ Class, and Preferred Term |
| 14.3.1.8.2 | Safety | Summary of Treatment Emergent Adverse Events by Maximum Severity and Preferred Term |
| 14.3.1.9.1 | Safety | Summary of Pruritus Treatment Emergent Adverse Events by System Organ Class and Preferred Term |
| 14.3.1.9.2 | Safety | Summary of Pruritus Treatment Emergent Adverse Events by Preferred Term |
| 14.3.1.9.3 | Safety | Treatment-Emergent Pruritus Event Days |

| | | |
|---------------|--------|---|
| 14.3.1.9.4 | Safety | Time to Onset of First Treatment Emergent Pruritus |
| 14.3.1.9.5 | Safety | Time to Onset of Most Severe Treatment Emergent Pruritus |
| 14.3.1.9.6 | Safety | Time to Resolution of the Most Severe Treatment Emergent Pruritus |
| 14.3.1.10.1 | Safety | Summary of Dyslipidaemia Treatment Emergent Adverse Events by System Organ Class and Preferred Term |
| 14.3.1.10.2 | Safety | Summary of Dyslipidaemia Treatment Emergent Adverse Events by Preferred Term |
| 14.3.1.10.3 | Safety | Time to Onset of First Treatment Emergent Dyslipidaemia |
| 14.3.1.11.1 | ITT | Summary of On-Study Procedures by System Organ Class and Preferred Term |
| 14.3.1.11.2 | ITT | Summary of On-Study Procedures by Preferred Term |
| 14.3.4 | | Clinical Laboratory Evaluations |
| 14.3.4.1 | Safety | Summary of Hematology and Coagulation by Treatment and Visit |
| 14.3.4.1.2 | Safety | Hematology and Coagulation Shift Analysis by Treatment and Visit |
| 14.3.4.2.1 | Safety | Summary of Serum Chemistry by Treatment and Visit – SI Units |
| 14.3.4.2.2 | Safety | Summary of Serum Chemistry by Treatment and Visit – CV Units |
| 14.3.4.2.3 | Safety | Serum Chemistry Shift Analysis by Treatment and Visit |
| 14.3.4.3 | Safety | Summary of Apolipoprotein by Treatment and Visit |
| 14.3.4.4 | Safety | Summary of Nuclear Magnetic Resonance Lipoprotein Panel by Treatment and Visit |
| 14.3.4.5 | Safety | NMR Lipoprotein Shift Analysis by Treatment and Visit |
| 14.3.4.6 | Safety | Summary of Vital Signs by Treatment and Visit |
| 14.3.4.7 | Safety | Electrocardiogram Shift from Baseline by Treatment |

List of Figures

| Figure Number | Population | Figure Title |
|----------------|------------|---|
| 14.2 | | Efficacy Data |
| 14.2.1.1 | PK | Individual Plasma Concentration of OCA (Unconjugated) Over Time |
| 14.2.1.2 | PK | Individual Plasma Concentration of Glyco-OCA Over Time |
| 14.2.1.3 | PK | Individual Plasma Concentration of Tauro-OCA Over Time |
| 14.2.1.4 | PK | Individual Plasma Concentration of Total OCA Over Time |
| 14.2.2.1 | PK | Mean (SD) Plasma Concentration of OCA (Unconjugated) Over Time |
| 14.2.2.2 | PK | Mean (SD) Plasma Concentration of Total Glyco-OCA Over Time |
| 14.2.2.3 | PK | Mean (SD) Plasma Concentration of Total Tauro-OCA Over Time |
| 14.2.2.4 | PK | Mean (SD) Plasma Concentration of Total OCA Over Time |
| 14.2.3.1.1.1 | PK | Scatter Plot of Week 12 ALP versus Total OCA AUC ₀₋₆ |
| 14.2.3.1.1.2 | PK | Scatter Plot of Week 24 ALP versus Total OCA AUC ₀₋₆ |
| 14.2.3.1.2.1 | PK | Scatter Plot of Week 12 Change from Baseline in ALP versus Total OCA AUC ₀₋₆ |
| 14.2.3.1.2.2 | PK | Scatter Plot of Week 24 Change from Baseline in ALP versus Total OCA AUC ₀₋₆ |
| 14.2.3.2.1.1 | PK | Scatter Plot of Week 12 Total Bile Acids versus Total OCA AUC ₀₋₆ |
| 14.2.3.2.1.2 | PK | Scatter Plot of Week 24 Total Bile Acids versus Total OCA AUC ₀₋₆ |
| 14.2.3.2.2.1 | PK | Scatter Plot of Week 12 Change from Baseline in Total Bile Acids versus Total OCA AUC ₀₋₆ |
| 14.2.3.2.2.2 | PK | Scatter Plot of Week 24 Change from Baseline in Total Bile Acids versus Total OCA AUC ₀₋₆ |
| 14.2.3.3.1.1.1 | PK | Scatter Plot of Week 12 UCDA (conjugated) versus Total OCA AUC ₀₋₆ |
| 14.2.3.3.1.1.2 | PK | Scatter Plot of Week 12 UCDA (unconjugated) versus Total OCA AUC ₀₋₆ |
| 14.2.3.3.1.2.1 | PK | Scatter Plot of Week 24 UCDA (conjugated) versus Total OCA AUC ₀₋₆ |
| 14.2.3.3.1.2.2 | PK | Scatter Plot of Week 24 UCDA (unconjugated) versus Total OCA AUC ₀₋₆ |
| 14.2.3.3.2.1.1 | PK | Scatter Plot of Week 12 Change from Baseline in UCDA (conjugated) versus Total OCA AUC ₀₋₆ |
| 14.2.3.3.2.1.2 | PK | Scatter Plot of Week 12 Change from Baseline in UCDA (unconjugated) versus Total OCA AUC ₀₋₆ |

| | | |
|----------------|----|---|
| 14.2.3.3.2.2.1 | PK | Scatter Plot of Week 24 Change from Baseline in UCDA (conjugated) versus Total OCA AUC ₀₋₆ |
| 14.2.3.3.2.2.2 | PK | Scatter Plot of Week 24 Change from Baseline in UCDA (unconjugated) versus Total OCA AUC ₀₋₆ |
| 14.2.3.4.1.1.1 | PK | Scatter Plot of Week 12 CDCA (conjugated) versus Total OCA AUC ₀₋₆ |
| 14.2.3.4.1.1.2 | PK | Scatter Plot of Week 12 CDCA (unconjugated) versus Total OCA AUC ₀₋₆ |
| 14.2.3.4.1.2.1 | PK | Scatter Plot of Week 24 CDCA (conjugated) versus Total OCA AUC ₀₋₆ |
| 14.2.3.4.1.2.2 | PK | Scatter Plot of Week 24 CDCA (unconjugated) versus Total OCA AUC ₀₋₆ |
| 14.2.3.4.2.1.1 | PK | Scatter Plot of Week 12 Change from Baseline in CDCA (conjugated) versus Total OCA AUC ₀₋₆ |
| 14.2.3.4.2.1.2 | PK | Scatter Plot of Week 12 Change from Baseline in CDCA (unconjugated) versus Total OCA AUC ₀₋₆ |
| 14.2.3.4.2.2.1 | PK | Scatter Plot of Week 24 Change from Baseline in CDCA (conjugated) versus Total OCA AUC ₀₋₆ |
| 14.2.3.4.2.2.2 | PK | Scatter Plot of Week 24 Change from Baseline in CDCA (unconjugated) versus Total OCA AUC ₀₋₆ |
| 14.2.3.5.1.1.1 | PK | Scatter Plot of Week 12 LCA (conjugated) versus Total OCA AUC ₀₋₆ |
| 14.2.3.5.1.1.2 | PK | Scatter Plot of Week 12 LCA (unconjugated) versus Total OCA AUC ₀₋₆ |
| 14.2.3.5.1.2.1 | PK | Scatter Plot of Week 24 LCA (conjugated) versus Total OCA AUC ₀₋₆ |
| 14.2.3.5.1.2.2 | PK | Scatter Plot of Week 24 LCA (unconjugated) versus Total OCA AUC ₀₋₆ |
| 14.2.3.5.2.1.1 | PK | Scatter Plot of Week 12 Change from Baseline in LCA (conjugated) versus Total OCA AUC ₀₋₆ |
| 14.2.3.5.2.1.2 | PK | Scatter Plot of Week 12 Change from Baseline in LCA (unconjugated) versus Total OCA AUC ₀₋₆ |
| 14.2.3.5.2.2.1 | PK | Scatter Plot of Week 24 Change from Baseline in LCA (conjugated) versus Total OCA AUC ₀₋₆ |
| 14.2.3.5.2.2.2 | PK | Scatter Plot of Week 24 Change from Baseline in LCA (unconjugated) versus Total OCA AUC ₀₋₆ |
| 14.2.3.6.1.1.1 | PK | Scatter Plot of Week 12 CA (conjugated) versus Total OCA AUC ₀₋₆ |
| 14.2.3.6.1.1.2 | PK | Scatter Plot of Week 12 CA (unconjugated) versus Total OCA AUC ₀₋₆ |

| | | |
|----------------|----|--|
| 14.2.3.6.1.2.1 | PK | Scatter Plot of Week 24 CA (conjugated) versus Total OCA AUC ₀₋₆ |
| 14.2.3.6.1.2.2 | PK | Scatter Plot of Week 24 CA (unconjugated) versus Total OCA AUC ₀₋₆ |
| 14.2.3.6.2.1.1 | PK | Scatter Plot of Week 12 Change from Baseline in CA (conjugated) versus Total OCA AUC ₀₋₆ |
| 14.2.3.6.2.1.2 | PK | Scatter Plot of Week 12 Change from Baseline in CA (unconjugated) versus Total OCA AUC ₀₋₆ |
| 14.2.3.6.2.2.1 | PK | Scatter Plot of Week 24 Change from Baseline in CA (conjugated) versus Total OCA AUC ₀₋₆ |
| 14.2.3.6.2.2.2 | PK | Scatter Plot of Week 24 Change from Baseline in CA (unconjugated) versus Total OCA AUC ₀₋₆ |
| 14.2.3.7.1.1.1 | PK | Scatter Plot of Week 12 DCA (conjugated) versus Total OCA AUC ₀₋₆ |
| 14.2.3.7.1.1.2 | PK | Scatter Plot of Week 12 DCA (unconjugated) versus Total OCA AUC ₀₋₆ |
| 14.2.3.7.1.2.1 | PK | Scatter Plot of Week 24 DCA (conjugated) versus Total OCA AUC ₀₋₆ |
| 14.2.3.7.1.2.2 | PK | Scatter Plot of Week 24 DCA (unconjugated) versus Total OCA AUC ₀₋₆ |
| 14.2.3.7.2.1.1 | PK | Scatter Plot of Week 12 Change from Baseline in DCA (conjugated) versus Total OCA AUC ₀₋₆ |
| 14.2.3.7.2.1.2 | PK | Scatter Plot of Week 12 Change from Baseline in DCA (unconjugated) versus Total OCA AUC ₀₋₆ |
| 14.2.3.7.2.2.1 | PK | Scatter Plot of Week 24 Change from Baseline in DCA (conjugated) versus Total OCA AUC ₀₋₆ |
| 14.2.3.7.2.2.2 | PK | Scatter Plot of Week 24 Change from Baseline in DCA (unconjugated) versus Total OCA AUC ₀₋₆ |
| 14.2.3.2.1.1 | PK | Scatter Plot of Week 12 C4 versus Total OCA AUC ₀₋₆ |
| 14.2.3.2.1.2 | PK | Scatter Plot of Week 24 C4 versus Total OCA AUC ₀₋₆ |
| 14.2.3.8.1.1 | PK | Scatter Plot of Week 12 Change from Baseline in C4 versus Total OCA AUC ₀₋₆ |
| 14.2.3.8.1.2 | PK | Scatter Plot of Week 24 Change from Baseline in C4 versus Total OCA AUC ₀₋₆ |
| 14.2.3.8.2.1 | PK | Scatter Plot of Week 12 Change from Baseline in C4 versus Total OCA AUC ₀₋₆ |
| 14.2.3.8.2.2 | PK | Scatter Plot of Week 24 Change from Baseline in C4 versus Total OCA AUC ₀₋₆ |

List of Data Listings

| Listing Number | Listing Title |
|-----------------------|--|
| 16.2 | Subject Data Listings |
| 16.2.1 | Discontinued subjects |
| 16.2.1.1 | Analysis Populations |
| 16.2.1.2 | Subject Disposition |
| 16.2.2 | Protocol deviations |
| 16.2.2.1 | Protocol Deviations |
| 16.2.2.2 | Inclusion and Exclusion Criteria Findings |
| 16.2.4 | Demographic data |
| 16.2.4.1 | Demographics and Baseline Characteristics |
| 16.2.4.2 | PSC Disease History |
| 16.2.4.3 | Medical History |
| 16.2.5 | Compliance and/or drug concentration data |
| 16.2.5.1 | Investigational Product Accountability |
| 16.2.5.2 | Investigational Product Exposure |
| 16.2.5.3 | UDCA Administration |
| 16.2.5.4 | Concomitant Medications |
| 16.2.5.5.1 | Plasma Concentration Collection Information |
| 16.2.5.5.2 | Plasma Concentration Data for OCA, Glyco-OCA, Tauro-OCA, and Total OCA |
| 16.2.5.5.3 | Plasma PK Parameters for OCA, Glyco-OCA, Tauro-OCA, and Total OCA |
| 16.2.5.6.1 | Bile Acids and Bile Acid Subcomponents |
| 16.2.5.6.2 | Total Bile Acids and Total Endogenous Bile Acids |
| 16.2.6 | Individual efficacy response data |
| 16.2.6.1 | Alkaline Phosphatase |
| 16.2.6.2 | Hepatic Biochemistry and Indices of Function |
| 16.2.6.3 | Markers of Hepatic and GI Inflammation and Disease |
| 16.2.6.4 | Transient Elastography |
| 16.2.6.5 | Enhanced Liver Fibrosis Score and Components |
| 16.2.6.6 | Farnesoid X Receptor Activity |
| 16.2.6.7.1 | Pruritus Visual Analogue Scale Scores |
| 16.2.6.7.2 | Pruritus 5-D Itch Scores |

| | |
|---------------|--|
| 16.2.6.8 | Partial Mayo Score |
| 16.2.6.9 | Chron's Disease Activity Index Score |
| 16.2.6.10 | Transient Elastography |
| 16.2.7 | Adverse events listings |
| 16.2.7.1 | Adverse Events |
| 16.2.7.2 | Serious Adverse Events |
| 16.2.7.3 | Severe Adverse Events |
| 16.2.7.4 | Adverse Events Leading to Investigational Product Withdrawal or Study Discontinuation |
| 16.2.7.5 | Adverse Events Related to Investigational Product |
| 16.2.7.6 | Adverse Events Leading to Investigational Product Withdrawal |
| 16.2.7.7 | Adverse Events Leading to Investigational Study Discontinuation |
| 16.2.7.8 | Adverse Events Leading to Death |
| 16.2.8 | Listing of individual laboratory measurements by subject, when required by regulatory authorities |
| 16.2.8.1 | Laboratory Sample Collection |
| 16.2.8.2 | Hematology and Coagulation |
| 16.2.8.3.1 | Serum Chemistry – SI Units |
| 16.2.8.3.2 | Serum Chemistry – CV Units |
| 16.2.8.4 | Urinalysis |
| 16.2.8.5 | Apolipoprotein and NMR Lipoprotein |
| 16.2.8.6.1 | Laboratory Reference/Normal Ranges – SI Units |
| 16.2.8.6.2 | Laboratory Reference/Normal Ranges – CV Units |
| 16.2.9 | Additional Safety Listings |
| 16.2.9.1 | Vital Signs |
| 16.2.9.2 | 12-lead Electrocardiograms (ECGs) |
| 16.2.9.3 | Pregnancy Test Results |
| 16.2.9.4 | Historical and On-Study Procedures |
| 16.2.9.5 | Subject Visit Information |
| 16.2.9.6 | Subject Reconsent |
| 16.2.9.7 | Comments |

APPENDIX B. DYSLIPIDEMIA PREFERRED TERMS AND ASSOCIATED CODES

| Preferred Term | Code |
|---|----------|
| Acquired lipoatrophic diabetes | 10073667 |
| Acquired mixed hyperlipidaemia | 10071236 |
| Apolipoprotein B/Apolipoprotein A-1 ratio increased | 10065516 |
| Autoimmune hyperlipidaemia | 10071577 |
| Blood cholesterol abnormal | 10005423 |
| Blood cholesterol decreased | 10005424 |
| Blood cholesterol esterase increased | 10071304 |
| Blood cholesterol increased | 10005425 |
| Blood triglycerides abnormal | 10005837 |
| Blood triglycerides decreased | 10005838 |
| Blood triglycerides increased | 10005839 |
| Diabetic dyslipidaemia | 10070901 |
| Dyslipidaemia | 10058108 |
| Familial hypertriglyceridaemia | 10059183 |
| Fat overload syndrome | 10074028 |
| High density lipoprotein abnormal | 10020051 |
| High density lipoprotein decreased | 10020060 |
| High density lipoprotein increased | 10020061 |
| Hypercholesterolaemia | 10020603 |
| Hyperlipidaemia | 10062060 |
| Hypertriglyceridaemia | 10020869 |
| Hypo HDL cholesterolaemia | 10068961 |
| Hypotriglyceridaemia | 10021128 |
| Intermediate density lipoprotein decreased | 10064237 |
| Intermediate density lipoprotein increased | 10064236 |
| LDL/HDL ratio decreased | 10052338 |
| LDL/HDL ratio increased | 10049030 |
| Lipid metabolism disorder | 10061227 |
| Lipids abnormal | 10024588 |
| Lipids decreased | 10024591 |

| | |
|--|----------|
| Lipids increased | 10024592 |
| Lipoprotein (a) abnormal | 10054023 |
| Lipoprotein (a) decreased | 10054021 |
| Lipoprotein (a) increased | 10054009 |
| Low density lipoprotein abnormal | 10024901 |
| Low density lipoprotein decreased | 10024909 |
| Low density lipoprotein increased | 10024910 |
| Non-high-density lipoprotein cholesterol decreased | 10064235 |
| Non-high-density lipoprotein cholesterol increased | 10063967 |
| Remnant hyperlipidaemia | 10038316 |
| Remnant-like lipoprotein particles increased | 10073041 |
| Total cholesterol/HDL ratio abnormal | 10058633 |
| Total cholesterol/HDL ratio decreased | 10058631 |
| Total cholesterol/HDL ratio increased | 10058630 |
| Type I hyperlipidaemia | 10060749 |
| Type II hyperlipidaemia | 10045254 |
| Type IIa hyperlipidaemia | 10045261 |
| Type IIb hyperlipidaemia | 10045263 |
| Type III hyperlipidaemia | 10060751 |
| Type IV hyperlipidaemia | 10060753 |
| Type V hyperlipidaemia | 10060755 |
| Very low density lipoprotein abnormal | 10047352 |
| Very low density lipoprotein decreased | 10047360 |
| Very low density lipoprotein increased | 10047361 |

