Lipoprotein changes have also been observed with OCA dosing in subjects with PBC (including a decrease in high-density lipoprotein [HDL]). The clinical significance of these lipid findings remains unclear and is being studied further. Notably, despite an observed decrease in HDL levels, they generally remained within normal limits. The relevance of these findings to subjects with PSC is unclear and will be investigated further in this trial.

In addition, the Data Safety Monitoring Committee (DSMC) will review safety data from the present trial as well as other ongoing OCA trials at approximately quarterly intervals but at least every 6 months. Adjustments to or stopping of the protocol-defined doses may be considered based on DSMC evaluation of OCA safety and tolerability as noted in [Section 6.4.3](#).

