10.3.2. Dyslipidaemia

AE lipid profile changes, defined in the Dyslipidaemia SMQ, will be reported. See [Appendix B](#) for a list of the preferred terms and their associated codes. These events will be summarized separately by the MedDRA system organ class (SOC), treatment group, and preferred term (PT) as a subset of all TEAEs.

In order to explore the relationship between dyslipidaemia and the investigational product, the following time-to-event analyses will be performed:

- Time to first onset of treatment-emergent dyslipidaemia
 - The time to the start of the first episode will be calculated by date of onset of first episode – date of first dose of investigational product + 1.

The analysis of time to event will include the number of subjects with the event (first onset) and the number of subjects without the event (censored), descriptive statistics of time for those with

an event, and range in days for all subjects. Kaplan-Meier (KM) estimates will be calculated by treatment group. The quartiles, including the median time-to-event and their respective 2-sided 95% CIs, will be presented. KM estimates will be plotted as a “survival curve” for each treatment group, with the number at risk identified. The comparison of OCA to placebo will be summarized using a log-rank test stratified by randomization strata factor.

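### The time-to-first-dyslipidaemia curve and log-rank test in SAP 10.3.2 count lipid changes in both directions as one event, so that result does not measure lipid harm

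*SAP*

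**What the plan says.** SAP 10.3 names two adverse events of special interest, pruritus and dyslipidaemia. For the second, SAP 10.3.2 states: "AE lipid profile changes, defined in the Dyslipidaemia SMQ, will be reported". It refers to Appendix B for the terms. The one time-to-event endpoint is "Time to first onset of treatment-emergent dyslipidaemia", with Kaplan-Meier estimates and this test: "The comparison of OCA to placebo will be summarized using a log-rank test stratified by randomization strata factor". No restriction by direction is given.

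Appendix B lists "High density lipoprotein decreased" and "High density lipoprotein increased" as adjacent entries. "Low density lipoprotein decreased" stands next to its increased counterpart. Triglycerides, cholesterol, VLDL, IDL, non-HDL cholesterol, lipoprotein (a), lipids, and the LDL/HDL and total cholesterol/HDL ratios also appear in both directions.

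Protocol 4.5 reports lipoprotein changes with OCA in PBC, "including a decrease in high-density lipoprotein [HDL"]. It calls their relevance to PSC unclear and says that the trial will look into it.

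**The concern.** Safety is a primary objective, and SAP 10.3.2 gives its purpose as exploring how dyslipidaemia relates to the investigational product. A reader of the curve and p-value will take an event to be a lipid harm. As defined, a subject whose HDL rose and a subject whose HDL fell have the same event.

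Two errors follow. If favourable reports occur at similar rates in both arms, or more often on placebo, they dilute a real adverse difference. If they occur mainly on OCA, the test can turn a non-harm into an apparent harm.

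**Working it through.** **Count of Appendix B.** There are 54 terms.
- 12 run opposite to the usual adverse direction: cholesterol, triglycerides, lipids, LDL, VLDL, IDL, non-HDL cholesterol and lipoprotein (a) decreased; the LDL/HDL and total cholesterol/HDL ratios decreased; hypotriglyceridaemia; HDL increased.
- 8 are *abnormal* terms with no direction.
- 54 − 12 − 8 = 34 remain. Of these, 2 specifically denote low HDL: HDL decreased and Hypo HDL cholesterolaemia.

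The figure of 12 is an upper count. The SAP labels no term favourable, and *lipids decreased* or *blood cholesterol decreased* could reflect falling HDL.

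**Inputs for size.** Protocol 6.3 gives 25 subjects per group. The documents give no lipid event rate, event count or power, so there is no planned figure to reproduce and every rate below is an assumption. One OCA arm is compared with placebo. Adverse (a) and favourable (f) events are taken as independent, so the pooled risk in an arm is p = 1 − (1 − a)(1 − f).

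**Methods.**
- (A) Two-sided 5% two-proportion z-test with pooled variance, power by exact enumeration over 25 + 25 subjects.
- (B) Log-rank approximation: HR = ln(1 − p₁)/ln(1 − p₀), expected events D = 25(p₁ + p₀), power = Φ(|ln HR|·√(D/4) − 1.96).

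**Worked cases for B.**
- Adverse terms only, 30% against 5%: HR = 0.3567/0.0513 = 6.95; D = 25 × 0.35 = 8.75; 1.939 × 1.479 − 1.96 = 0.908; power 82%.
- Favourable 5% added in each arm: p₁ = 1 − 0.70 × 0.95 = 0.335; p₀ = 1 − 0.95 × 0.95 = 0.0975; HR 3.98; D = 10.8; power 62%.

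| Adverse, OCA vs placebo | Favourable, OCA vs placebo | Pooled risk | A | B |
|---|---|---|---|---|
| 30% vs 5% | none | 30.0% vs 5.0% | 71% | 82% |
| 30% vs 5% | 1% vs 1% | 30.7% vs 6.0% | 68% | 77% |
| 30% vs 5% | 2% vs 2% | 31.4% vs 6.9% | 65% | 73% |
| 30% vs 5% | 5% vs 5% | 33.5% vs 9.8% | 57% | 62% |
| 30% vs 5% | 5% vs 10% | 33.5% vs 14.5% | 37% | 38% |
| 15% vs 5% | none | 15.0% vs 5.0% | 21% | 25% |
| 15% vs 5% | 2% vs 2% | 16.7% vs 6.9% | 19% | 21% |
| 5% vs 5% | 30% vs 5% | 33.5% vs 9.8% | 57% | 62% |

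The last row is the false signal: adverse terms do not differ, yet the pooled test is significant 57% of the time by A, against 2% on adverse terms alone. A simulated unstratified log-rank test gave 70%, 56%, 35% and 56% for the rows with favourable reports of none, 5% vs 5%, 5% vs 10% and 30% vs 5%. B is optimistic with about nine events. None of the methods applies the planned stratification.

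**Where direction survives.** SAP 10.3.2 and Table 14.3.1.10.2 give the events by preferred term. SAP 10.4 gives fasted lipoprotein values and change from Baseline by arm, with low-normal-high shifts for serum chemistry (Table 14.3.4.2.3). Table 14.3.4.5 gives NMR lipoprotein shifts.

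**The case against.** **HDL lowering is measured elsewhere.** It is a laboratory effect, and the outputs just listed show it with its direction. This stands. A reader might infer that the pooled definition hides the HDL risk from the safety report. The documents do not support that; the defect is confined to one curve and one p-value.

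**It may not be the only formal comparison.** A reader might also infer that no other between-group lipid test is planned. SAP 6.2.4 describes a repeated-measures model for clinical laboratory values, with treatment differences in its sample code, and Protocol 11.2.5 puts HDL, LDL, VLDL and triglycerides in serum chemistry. SAP Appendix A, however, lists no such table for lipids. The text is unclear, so the stronger claim fails.

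**Favourable changes are seldom adverse events.** Protocol 11.1.1.1 requires an untoward occurrence, and nothing in the documents supports favourable rates of 5% or more. This limits the size considerably. It does not remove the point: the same section allows an abnormal laboratory finding as an adverse event, and serum chemistry is drawn at every double-blind visit.

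**The full SMQ is a coherent, prespecified choice.** Protocol 4.5 speaks of lipoprotein changes generally, with HDL decrease as an example, and adds that HDL generally stayed within normal limits. The analysis is exploratory, and SAP 6.2.7 attaches no multiplicity control or decision to it. This supports keeping the full list for incidence. It does not make a curve that mixes both directions readable as harm.

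**Dropping 12 terms would not isolate low HDL.** Correct: 54 − 12 = 42 terms would remain, with low HDL still pooled with raised LDL and triglycerides. The fix therefore needs a separate low-HDL set.

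**Conclusion.** The point holds for the Kaplan-Meier and log-rank analysis of SAP 10.3.2, and for the descriptive time to most severe event in SAP 10.3, which draws on the same terms. These outputs treat opposite lipid changes as one event and cannot be read as showing harm.

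The effect is small if favourable reports are rare: about 3 percentage points of power at 1% per arm and 6 at 2% per arm in the 30% against 5% case, by method A. It becomes material only if such reports reach about 5% per arm or differ between arms. The 57% false-signal figure needs favourable changes reported as adverse events in 30% of OCA subjects. It shows what the definition permits and is not a forecast. All of this rests on assumed rates and on independence of the two kinds of event. The point is a modest one that should be corrected because the correction is cheap.

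**What to change.** Before the double-blind database is locked and unblinded:

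1. Keep the full SMQ for the incidence tables.
2. Add a direction column to Appendix B (adverse, opposite, undetermined). The sponsor should classify the 8 *abnormal* terms and the ambiguous ones, such as *lipids decreased* and *blood cholesterol decreased*, and record the reasons.
3. In SAP 10.3.2, base the time-to-event and log-rank analysis on adverse-direction terms, and apply the same set to time to most severe event in 10.3.
4. Show low HDL (HDL decreased, Hypo HDL cholesterolaemia) as its own event set.
5. If a full-SMQ curve is kept, label it as any lipid change.

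The cost is one column in an appendix, slightly fewer events in the main curve, and one or two extra exploratory outputs. Trial conduct and data collection do not change.
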